## 12.4 Analyses

### 12.4.1 *Baseline Characteristics*

Demographic and baseline disease characteristic data will be summarized. Data to be tabulated will include at least demographic features such as sex, age, and race, as well as disease-specific status and medical history.

Categorical data will be summarized using counts and percentages based on non-missing values. For continuous variables, the mean, median, standard deviation, minimum and maximum values will be presented. Data will be summarized according to the defined populations for analysis.

### 12.4.2 *Safety Analyses*

Exposure to investigational product and reasons for discontinuation of study treatment will be tabulated. All treatment-emergent AEs will be coded according to the system organ class and preferred term using the Medical Dictionary for Regulatory Affairs (MedDRA®), and will be tabulated by number and percent of subjects, and according to relationship to the investigational product, severity, and seriousness. ‘Treatment-emergent’ is defined as any AE that occurs during or after administration of the first dose of investigational product through the evaluation period for safety defined above, regardless of relationship to investigational product; or any event that is present at baseline that worsens in intensity or is subsequently considered to be drug related by the investigator.

Deaths, SAEs, and AEs resulting in patient discontinuation will be listed. Laboratory parameters, vital signs, and physical examination data will be summarized by visit. Data listings will be presented by visit.

Toxicity stopping rules ([Jennison and Turnbull, 2000](#); [Ivanova et al, 2005](#)), when applicable, will be determined based on a clinical assessment made by the SRC after a formal evaluation of safety data after every 5 subjects with HER2- disease have completed one cycle of Ad-RTS-hIL-12 immunotherapy. The SRC will review safety data separately for subjects with HER2+ disease to assess toxicity after the first 5 HER2+ subjects complete one cycle of Ad-RTS-hIL-12 immunotherapy.

The first stopping rule is based on related, treatment refractory Grade 3 or 4 adverse events. A rate of 50% is deemed unacceptable, a rate of 25% is deemed acceptable. The boundaries to stop the study are given as follows:

- If 4 of the first 5 patients have related, treatment refractory Grade 3 or 4 AE, stop the study.
- If 6 of the first 10 patients have related, treatment refractory Grade 3 or 4 AE, stop the study.
- If 8 of the first 15 patients have related, treatment refractory Grade 3 or 4 AE, stop the study.

- If 9 of the first 20 patients have related, treatment refractory Grade 3 or 4 AE, stop the study.
- If 11 of the first 25 patients have related, treatment refractory Grade 3 or 4 AE, stop the study.
- If 12 of the first 30 patients have related, treatment refractory Grade 3 or 4 AE, stop the study.
- If 14 of the first 35 patients have related, treatment refractory Grade 3 or 4 AE, stop the study.
- If 15 of the first 40 patients have related, treatment refractory Grade 3 or 4 AE, stop the study.

#### **12.4.3           *Efficacy Analyses***

Efficacy will be based on the tumor response at 12 weeks.

##### **12.4.3.1           Tumor response**

Tumor response (CR, PR, SD, and PD) will be determined according to RECIST v.1.1 (see [Section 9](#)).

##### **12.4.3.2           Progression rate**

The proportion failed by 12 weeks is denoted as the progression rate survival and is derived based on the sum of progression events, death events and subjects who discontinue the trial due to an AE.

The second stopping rule is based on the progression rate during the 12 weeks of immunotherapy. A progression rate of 50% is deemed acceptable, while an 80% rate is deemed unacceptable. The boundaries to stop the study using a repeated significance testing approach are given as follows:

- If 5 of the first 5 patients progress, stop the study.
- If 9 of the first 10 patients progress, stop the study.
- If 12 of the first 15 patients progress, stop the study.
- If 15 of the first 20 patients progress, stop the study.
- If 18 of the first 25 patients progress, stop the study.
- If 20 of the first 30 patients progress, stop the study.
- If 23 of the first 35 patients progress, stop the study.
- If 26 of the first 40 patients progress, stop the study.

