This is a single-arm, single-center phase Ib/II study to examine the safety, tolerability and preliminary efficacy of one cycle of Ad-RTS-hIL-12 immunotherapy in women with advanced breast cancer and pre-study SD or PR after completion of a minimum 12 week course of standard first-, second-, or third-line chemotherapy. The patient population will include patients with locally advanced or metastatic breast cancer of all subtypes. The safety of this therapy and the preliminary evidence of efficacy will guide further studies. Subjects who have progressive disease (PD) or a (CR) after the standard chemotherapy are not eligible for the study. Following

entry into the trial, patients will go on a treatment holiday from chemotherapy and enter an immunotherapy phase of treatment. Continuation of HER2-targeted antibody therapy is permitted during this immunotherapy phase for women with HER2+ disease. Scans will be conducted at 6 and 12 weeks after the start of Ad-RTS-hIL-12 immunotherapy to determine tumor response. Radiographic PD at week 6 must be confirmed at least 4 weeks later, either at week 12 or earlier if clinically necessitated, except in cases of unequivocal progression.

The assessment of response will be based on Response Evaluation Criteria in Solid Tumors (RECIST) v1.1 using tumor measurements from contrast-enhanced computed tomography (CT). Tumor response will also be assessed by Immune-Related Response Criteria (irRC) (Wolchok et al, 2009). Eligible subjects will also be asked to consent to allow ZIOPHARM to obtain scans and tumor measurements taken both a) prior to initiating the pre-study standard chemotherapy and b) after a minimum of 12 weeks of pre-study standard chemotherapy, and not more than 4 weeks prior to study enrollment, in order to confirm their SD, PR status.

For subjects with HER2- disease, the Ad-RTS-hIL-12 immunotherapy is intended to be given as a chemotherapy break, for example, to avoid intolerable or undesirable toxicity of the standard chemotherapy. Ad-RTS-hIL-12 immunotherapy must be started within 4 weeks of stopping the pre-study standard chemotherapy.

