#### **4.4 Withdrawal of Subjects from Study Treatment and/or Study**

The Sponsor may terminate this study at any time. The investigator and/or the subject have the right to terminate the subject's participation in the study at any time.

A subject **may** discontinue study treatment prematurely for any of the following reasons:

- The investigator determines further participation is not in subject's best interest (for example, subject experiences rapid clinical deterioration in the absence of confirmed disease progression)
- Subject has confirmed disease progression

A subject **MUST** discontinue study treatment in the event of any of the following:

- Subject request to end study treatment
- Any treatment-related AE(s) that meet withdrawal criteria
- Substantial noncompliance with study requirements
- Confirmed positive pregnancy test
- Any intercurrent illness that would, in the judgement of the investigator or Sponsor's medical monitor, affect assessments of clinical status to a significant degree and require discontinuation of protocol therapy

A subject **MUST** be withdrawn from the study in the event of any of the following:

- Withdrawal of informed consent for the study
- The Ad-RTS-hIL-12 injection was not received

NOTE: Any subject receiving veledimex will be included in the safety analysis group even if the Ad-RTS-hIL-12 injection was not received.

Every effort should be made to follow subjects who withdraw from study treatment for ongoing treatment-related AEs until resolved, no resolution is expected, or the study has ended.

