## 7 CONCOMITANT THERAPY

Information on concomitant medications, including all medications, blood products, vitamins, and other supplements, will be collected from the Screening visit through the end of the Initial Follow-up Period (Week 12). Any new anti-cancer therapy that is started prior to confirmation of a radiographic response of PD, should be collected and entered as a concomitant medication.

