#### **8.4.8 *Initial Follow-Up Period: Week 6***

- ECOG performance status
- Vital signs
- Physical examination
- Adverse events
- Weight
- Concomitant medications
- Hematology panel
- Serum chemistry panel
- Research bloods
- Tumor markers
- Tumor Biopsy
- Imaging studies for tumor response. If radiographic PD is detected at 6 weeks, PD must be confirmed with repeat imaging 4 weeks later. In case of slow tumor growth, the investigator may wait until confirmation of the PD at 12 weeks to resume chemotherapy. In case of unequivocal progression, the investigator may resume chemotherapy prior to 12 weeks and the subject will be considered as treatment failure at 12 weeks.

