#### **8.4.9 *Initial Follow-Up Period: Week 12***

- ECOG performance status
- Vital signs
- Physical examination
- Adverse events
- Weight
- Concomitant medications (including any new anti-cancer therapies)

- Hematology panel
- Serum chemistry panel
- Research bloods
- Tumor markers
- Imaging studies for tumor response

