#### **9.2.2.4.1      *Additional Notes Relevant to Designations of Disease Progression***

Per RECIST v.1.1, patients with a global deterioration of health status requiring discontinuation of treatment without objective evidence of disease progression should be reported as “symptomatic deterioration,” and every effort should be made to document objective progression

even after discontinuation of treatment. Symptomatic deterioration is not a descriptor of an objective response; it is a reason for stopping study therapy. The objective response of such subjects is to be determined by evaluation of target and non-target disease as shown in [Table 9.2.2.1-1](#) and [Table 9.2.2.2-1](#). In the current study, scans are to be done at week 6 and 12 weeks, and at any time deemed appropriate by the investigator (i.e., when progression is suspected). PD at week 6 must be confirmed at least 4 weeks later. The definition of progression rate for this study, is given in [Section 12.4.3.2](#).

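### The 12-week failure list gives no status to new anticancer therapy started before confirmed progression, so such subjects can go uncounted in the progression rate and its stopping rule

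*Protocol*

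**What the plan says.** Section 12.4.3.2 sets the proportion failed by 12 weeks as "derived based on the sum of progression events, death events and subjects who discontinue the trial due to an AE". Section 9.2.2.4.1 sends the reader to that section for the study's definition of progression rate. A rate of 50% is called acceptable and 80% unacceptable, and eight boundaries follow with fixed denominators from the first 5 to the first 40 patients, for example: "If 15 of the first 20 patients progress, stop the study".

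On confirmation, Section 8.4.8 says: "If radiographic PD is detected at 6 weeks, PD must be confirmed with repeat imaging 4 weeks later". Table 9.2.2.1-1 also makes confirmation at least 4 weeks later part of this study's PD definition. The synopsis waives it "except in cases of unequivocal progression", and Sections 3.1 and 8.4.8 class a subject who resumes chemotherapy early for unequivocal progression as a treatment failure at 12 weeks.

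On new therapy, Section 7 says: "Any new anti-cancer therapy that is started prior to confirmation of a radiographic response of PD, should be collected". Section 8.4.9 lists new anticancer therapies among the items recorded at Week 12. Neither section says how such a subject is scored. Section 7.2 bars other anticancer therapy only during study treatment.

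**The concern.** The rule exists to halt the study if too many subjects lose disease control during the chemotherapy break. A subject who starts other therapy before Week 12 because a scan looks worse has probably lost it. She is outside the three listed events unless progression is confirmed or unequivocal, she dies, or she leaves the trial for an AE. Two consequences follow.

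- Read literally, she fills a place among the first n patients without adding to the count.
- Her confirming or Week 12 scan is taken under the new therapy. A response to that therapy could be read as progression not confirmed, and she would be recorded as progression-free after the study product.

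Both lower the recorded progression rate and make the rule slower to act. Section 12.4.7 requires the SAP only before database lock, so it need not exist when the looks are taken.

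**Working it through.** **The plan's own figure.** Section 12.2 states a maximum exact 95% half-width of 0.16 at n = 40. The Clopper-Pearson interval is widest at 20 of 40: 0.338 to 0.662, half-width (0.662 − 0.338)/2 = 0.162. The figure is reproduced. The protocol states no alpha or power for the stopping rule, so there is none to check.

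**How each case is scored by Week 12**

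| Case | Status in the protocol |
|---|---|
| Progression confirmed | Failure (12.4.3.2) |
| Chemotherapy resumed for unequivocal progression | Failure (3.1, 8.4.8; confirmation waived in the synopsis) |
| Death, or leaving the trial for an AE | Failure (12.4.3.2) |
| New therapy on unconfirmed, non-unequivocal progression, or without progression | Recorded (7, 8.4.9), not scored |

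Only the last row is open.

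**Stopping rule.** Inputs from Section 12.4.3.2: looks at n = 5, 10, …, 40 with boundaries r = 5, 9, 12, 15, 18, 20, 23, 26. Let c be the probability that a subject is *counted* as failed. Then X(k) = X(k−1) + Binomial(5, c), and the study stops at the first k with X(k) ≥ r(k). P(ever stop) is the sum over k of P(stop at k). Expected n is the sum of n(k) × P(stop at k), plus 40 × P(never stop). The recursion is exact and ignores subjects enrolled while outcomes are awaited. As a check, P(stop at n = 5) at c = 0.80 is 0.80^5 = 0.328.

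**Under-counting.** Assume 80% is the failure rate *including* the unscored subjects, and that a share q of all subjects fails only by starting new therapy, with no listed event by Week 12. Then c = 0.80 − q. The protocol gives no q, so a range is assumed.

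| q | c | P(ever stop) | P(stop by n = 20) | Expected n |
|---|---|---|---|---|
| 0 | 0.800 | 0.995 | 0.838 | 14.0 |
| 2.5% | 0.775 | 0.985 | 0.762 | 15.9 |
| 5% | 0.750 | 0.963 | 0.675 | 18.0 |
| 10% | 0.700 | 0.861 | 0.491 | 22.9 |

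One subject can decide a look: at n = 20, 14 listed failures plus one unscored failure do not stop the study, whereas 15 do.

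**Effect of widening the list.** If instead 50% is the rate on the *current* list and q is added, c = 0.50 + q.

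| q | c | P(ever stop) | Expected n |
|---|---|---|---|
| 0 | 0.500 | 0.103 | 37.9 |
| 2.5% | 0.525 | 0.157 | 37.1 |
| 5% | 0.550 | 0.231 | 35.9 |
| 10% | 0.600 | 0.433 | 32.5 |

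The two tables attach the protocol's rates to different definitions. They are two separate what-ifs, not one scenario.

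**The case against.** The strongest reply is that Section 12.4.3.2 attaches 80% to the rate it has just defined. At a listed rate of 80% the rule stops with probability 0.995 and nothing is lost. That is correct: the loss in the first table exists only if 80% is meant to describe all subjects who fail.

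Second, the route may be rare. After Week 6 progression the protocol describes only waiting for confirmation or resuming chemotherapy early for unequivocal progression. The collection clause in Section 7 also came with the long-term follow-up amendment, so it reaches beyond Week 12. Both points limit the size. They do not close the gap: Section 8.4.9 asks for new therapies at Week 12 itself, and no passage scores them.

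Third, Section 12.4.3.2 speaks of progression events without the word confirmed, so an unconfirmed Week 6 finding might be counted. But Table 9.2.2.1-1 makes confirmation part of PD in this study, so the text at best supports two readings.

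Fourth, the SAP could classify such events. It could, but the protocol fixes the list and boundaries itself, and the looks may come first.

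A reader might also infer that clinical deterioration is wrongly left out. The documents do not support this. The example in Section 4.4, "subject experiences rapid clinical deterioration in the absence of confirmed disease progression", is a reason to stop study treatment, which is one injection and seven days of veledimex, not a reason to leave the study, so scans can continue. Section 9.2.2.4.1 states: "Symptomatic deterioration is not a descriptor of an objective response; it is a reason for stopping study therapy". It asks for every effort to document objective progression afterwards. The omission looks deliberate, and adding an investigator's judgement to an open-label, single-arm rate would be a trade-off.

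**Conclusion.** The point holds in a limited form. The failure list is closed, the protocol foresees and records an event outside it, and that event has no endpoint status although the protocol already treats its nearest neighbour, chemotherapy resumed for unequivocal progression, as failure. The rate and the looks can therefore be biased towards fewer failures.

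The size is illustrative. It rests on an assumed share, on that share being constant over enrolment and not recaptured by a listed event by Week 12, on affected subjects staying in the first n (the protocol does not say), and on 80% being the rate under the widened definition. At 2.5% uncounted, P(ever stop) moves only from 0.995 to 0.985. P(stop by n = 20) falls further, from 0.838 to 0.762, so the main effect is delay. Only towards 10% does failure to stop become material.

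It would be wrong to conclude that all early chemotherapy goes uncounted, or that the rule fails at the rate the protocol calls unacceptable. The first is contradicted by Sections 3.1 and 8.4.8. The second depends on a definition of 80% that the protocol does not give.

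**What to change.** In Section 12.4.3.2:

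- Count each subject once as failed by Week 12, at the first of: PD (including unequivocal PD without confirmation, as the synopsis and Sections 3.1 and 8.4.8 already provide), death, discontinuation of the trial due to an AE, or start of non-protocol anticancer therapy. Permitted anti-HER2 antibody therapy does not count as such a start.
- Use this one definition for both the progression rate and the stopping looks, and say that the 50% and 80% rates refer to it.
- State how non-evaluable subjects enter the first n.
- Do not make symptomatic deterioration a failure event by itself. Report it separately or as a sensitivity count.
- Restate the operating characteristics of the boundaries under this definition.

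This changes endpoint wording only and leaves clinical management as it is. The needed data are already collected, so the cost is a wording change and one recalculation. The downsides are a slightly less favourable rate and, if 50% was meant for the current list, more frequent stopping with unchanged boundaries: 0.157, 0.231 or 0.433 instead of 0.103 when 2.5, 5 or 10% of subjects are added. If that is not acceptable, the boundaries need to be reset.

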12.4.3.3 Progression-free Rate

Proportion of subjects who have 12-week progression free survival (proportion failed) after the start of Ad-RTS-hIL-12 immunotherapy.

12.4.3.4 ORR

The ORR is defined as the percentage of subjects who have CR or PR at 12 weeks after the start of Ad-RTS-hIL-12 immunotherapy.

12.4.3.5 DCR

The disease control rate is the proportion of subjects who have a CR, PR, or SD at 12 weeks after the start of Ad-RTS-hIL-12 immunotherapy.

12.4.3.6 Multi-Center Study

Not applicable. This is a single center study at the Memorial Sloan Kettering Cancer Center (MSKCC).

**12.4.4 *Adjustments for Covariates***

No adjustments for covariates will be made.

**12.4.5 *Procedures for Handling Missing, Unused, and Spurious Data***

No imputation of values for missing data will be performed. Standard clinical monitoring and data management practices will be used to ensure the integrity of data.

**12.4.6 *Interim Analysis***

See pre-specified stopping rules in [Section 12.4.2](#) and [Section 12.4.3.2](#).

**12.4.7 *Procedures for Reporting Deviations to Original Statistical Analysis Plan***

A formal statistical plan for the analysis and presentation of data from this study will be prepared prior to database lock. Deviations from the statistical analyses outlined in this protocol will be indicated in this plan; any further modifications will be noted in the final clinical study report.

## 13 STUDY MANAGEMENT

### 13.1 Electronic Case Report Forms and Source Documentation

For each subject, eCRFs and corresponding source records will be maintained at the clinical site. The Sponsor or designee will provide the study site with secure access to and sufficient training on the electronic data capture application, to permit site personnel to enter or correct information in the eCRFs for the subjects for whom they are responsible.

The eCRFs should be completed in a timely manner, and every effort should be made to have forms completed and up-to-date in anticipation of a visit by the Sponsor's monitor. Specific instructions will be provided to the site. All requested information must be entered on the eCRF in the spaces provided. If an item is not available or is not applicable, it should be documented as such; do not leave a space blank.

It is the investigator's responsibility to ensure the accuracy, completeness, clarity, and timeliness of the data reported in the subject's eCRF. Through the electronic data capture application, the investigator must provide formal approval of all subject information in the eCRFs and changes to the eCRFs to endorse the final submitted data for the subjects for whom he/she is responsible. The audit trail entry will show the user's identification information and the date and time of any corrections.

eCRF completion may be delegated to other study personnel; however, such delegation must be documented in writing. If, for any reason, certain data are lacking to complete an individual report form, the investigator will provide a written statement explaining the reasons for the lack of data.

Sponsor or designee will retain the eCRF data and corresponding audit trails. A copy of the final archival eCRF in the form of a compact disk or other electronic media will be placed in the investigator's study file.

### **13.2 Good Clinical Practice**

The study will be conducted in accordance with ethical principles that have their origin in the Declaration of Helsinki and are consistent with International Conference on Harmonization (ICH) Good Clinical Practice (GCP) guidelines, applicable regulatory requirements, and ZIOPHARM policies.

### **13.3 Sponsor Monitoring**

After satisfactory receipt of all necessary regulatory paperwork, the Sponsor's monitor will arrange that all study material be delivered to the study site at a mutually convenient time. An initiation visits by ZIOPHARM and its monitoring personnel will be made. At this meeting, all personnel expected to be involved in the conduct of the study will undergo an orientation to include review of study protocol, instruction for CRF completion and overall responsibilities, including those for drug accountability and study file maintenance.

Throughout the course of the study, the Sponsor's monitor will make frequent contact with the investigator, and this will include telephone and/or on-site visits. During these visits, CRFs will be reviewed for completeness and adherence to protocol. As part of the data audit, it is expected that source documents (e.g. hospital records, office records) will be made available for review by the monitor. The monitor also will perform drug accountability checks, and may periodically request review of the investigator's study file to assure completeness of documentation in all respects of study conduct.

Upon study completion, the monitor will arrange for a final review of the study files, after which the file should be secured by storage for the appropriate period as specified in [Section 13.5](#). The

investigator or appointed delegate will receive the Sponsor's representative during these on-site visits and will cooperate in providing the documents for inspection and responding to inquiries that may arise as part of this review. The investigator will also permit inspection of the study files by authorized representatives of the FDA.

